11.1.3 Serious Adverse Events

All AEs will be assessed as either serious or non-serious.

An SAE or serious adverse reaction is defined as any untoward medical occurrence that at any dose:

- Results in death
- Is immediately life threatening, (the term "life threatening" in the definition of "serious" refers to an event in which the subject is at risk of death at the time of the event; it does not refer to an event which hypothetically might have caused death if it were more severe)
- Requires in-patient hospitalization or prolongation of existing hospitalization (hospitalization for elective surgery for a condition present at Screening is not considered an AE)
- Results in persistent or significant disability/incapacity (permanent or substantial disruption of a person's ability to conduct normal life functions)
- Is a congenital anomaly/birth defect
- Is a medically important event that may not be immediately life threatening or result in death or hospitalization, but may jeopardize the subject and may require medical or surgical intervention to prevent any of the above listed outcomes

If the BCC surgery requires, as per standard of care, that the patient be hospitalized, then this hospitalization is not an SAE.

Note: A spontaneous abortion will be considered an SAE and must be reported per Reporting of SAEs under Section 11.1.6. Pregnancy in and of itself is not an SAE, but a subject who becomes pregnant must discontinue IP application immediately and the pregnancy will be followed to term (and ideally the child will be followed afterward if the subject consents) or termination. Any birth defect or other serious issue that may arise during the pregnancy or due to fetal exposure will be considered an SAE.

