8.3.2 Physical Examination and Vital Signs

Physical examinations (PEs) including vital signs (blood pressure, heart rate, respiration rate, and temperature), weight will be collected and reported. Height will be collected at the Baseline Visit only. Clinically significant changes from Baseline will be captured as AEs. Changes in BCC count will be captured separately as efficacy assessments and not as a PE assessment. Changes in BCC count or size will not constitute AEs.

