11 SAFETY INSTRUCTIONS AND GUIDANCE

11.1 Adverse Events

11.1.1 Definition of Adverse Event

An AE is any untoward medical occurrence in a subject administered a medicinal product and which does not necessarily have a causal relationship with the medicinal (investigational) product. AEs include any unfavorable and unintended illness, sign, symptom, clinically significant laboratory test abnormality, or disease associated with the use of a medicinal (investigational) product that has appeared or worsened during the course of the clinical trial, regardless of causal relationship to the medicinal (investigational) product under study.

Subjects will be questioned about any concurrent illness or sign or symptom. Any incidence of these signs or symptoms will be reported on the AE eCRF.

Vital signs and laboratory abnormalities are to be recorded as AEs only if they are clinically significant (for example: are symptomatic, requiring corrective treatment, leading to discontinuation or fulfilling a seriousness criterion). A laboratory abnormality that is part of an efficacy endpoint (e.g., histologic confirmation of BCC on a biopsy) is not to be reported as an AE.

An unexpected AE is one that is not listed in the Investigator's Brochure (IB) or is not listed at the specificity or severity that has been observed.

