12.7.2 Adverse Events

Subjects will be assessed for the occurrence of new and ongoing AEs. Listings of AEs will include the dates of onset and resolution (if resolved), maximum severity, seriousness, action taken regarding the IP, corrective treatment, outcome, and Investigator's assessment of causality. All AEs will be recorded and classified using terminology from the MedDRA. All reported TEAEs, defined as any AE with an onset on or after the date of first IP application, or worsening of an AE with an onset prior to first IP application, will be summarized, the number of subjects reporting TEAEs, system organ class, preferred term, severity, and relationship to IP. When summarizing TEAEs by severity or relationship to IP, each subject will be counted only once within a system organ class or a preferred term using the event with the greatest severity or causality, respectively, within each category. All reported SAEs will be summarized, the number of subjects reporting SAEs, system organ class, preferred term, severity, and relationship to IP.

All information pertaining to AEs noted during the study will be listed by subject and will include a verbatim description of the event as reported by the Investigator, as well as the preferred term, system organ class, start date, stop date (if stopped), seriousness, severity, action taken regarding the IP, corrective treatment, outcome and relationship to the IP. In addition, a listing of subjects who prematurely discontinue from the study due to AEs will be provided as well as a listing of subjects who reported an SAE.

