17.2 Diagnostic Criteria for Gorlin Syndrome

Diagnostic criteria for Gorlin syndrome includes major criterion #a plus 1 additional major criterion or plus 2 additional minor criteria listed below.

Major criteria:

- a. >2 histologically confirmed BCCs or 1 for subjects under age 20.
- b. Odontogenic keratocysts of the jaw confirmed histologically.
- c. ≥3 palmar and/or plantar pits seen at the Screening Visit.
- d. Bilamellar calcification of the falx cerebri present at less than 20 years old.
- e. Fused, bifid, or markedly splayed ribs.
- f. First degree relative with Gorlin Syndrome.
- g. PTCH1 mutation predicted to be of functional significance in normal tissue.

[figure not shown]
Minor criteria:

- a. Macrocephaly.
- b. Congenital malformations including frontal bossing, cleft lip or palate, "coarse face", moderate to severe hypertelorism.
- c. Skeletal abnormalities detectable clinically: Sprengel deformity, marked pectus deformity, or marked finger syndactyly.
- d. Skeletal abnormalities detectable radiographically: bridging of the sella turcica; vertebral abnormalities such as hemivertebrae, fusion or elongation of the vertebral bodies; modeling defects of the hands and feet; flame shaped lucencies of the hands or feet.
- e. Ovarian fibroma.
- f. Medulloblastoma (modification of criteria of V Kimonis et al Am J Med Genet 69: 299-308, 1997)

[figure not shown]

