6.4.2. Adverse Events

AEs will be graded by the investigator and coded using most recent version of the Medical Dictionary for Regulatory Activities (MedDRA).

Treatment-emergent adverse events (TEAEs) are those events with onset dates occurring during the on-treatment period for the first time, or if the worsening of an event is during the on-treatment period.

All analyses described **Error! Reference source not found.** will be based on TEAEs (started during the on-treatment period) if not otherwise specified. The AE listings will include all AEs (whether treatment-emergent or not). AEs outside the on-treatment period will be flagged in the listings.

- Related Adverse Events: adverse events with relationship to study treatment (as recorded on the AE eCRF page, Relationship with study treatment = Possibly / Probably / Definitely) reported by the investigator and those of unknown relationship (i.e., no answer to the question 'Relationship with study treatment'). Related AEs are those related to any study treatment.
- **Serious Adverse Events (SAE):** serious adverse events (as recorded on the AE eCRF page, Serious Adverse Event = Yes).
- Adverse Events Leading to Permanent Treatment Discontinuation: adverse events leading to permanent discontinuation of study treatment (as recorded on the AE eCRF page, Action taken with study treatment = Drug withdrawn).

• Adverse Events Leading to Death: adverse event leading to death (as recorded on the AE eCRF page, Outcome = Fatal).

Unless otherwise specified, AEs will be summarized by number and percentage of patients with the AE in the category of interest as described above, by primary SOC and PT in decreasing frequency based on the frequencies observed.

Each patient will be counted only once within each SOC or PT. If a patient experiences more than one AE within a SOC or PT for the same summary period, only the AE with the strongest relationship or the worst severity, as appropriate, will be included in the summaries of relationship and severity.

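### The elective-surgery exemption in Protocol 11.1.3 does not exclude conditions that worsened on study, so a narrow class of non-BCC events can miss SAE reporting

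*Protocol*

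**What the plan says.** Protocol 11.1.3 lists the criteria that make an AE serious. In-patient admission, or a longer existing admission, is one of them. That bullet carries a parenthesis: "hospitalization for elective surgery for a condition present at Screening is not considered an AE". Nothing in it refers to the timing of the decision to operate or to the course of the condition after Screening. A separate sentence in 11.1.3 says that admission for BCC surgery, where standard of care requires it, is not an SAE.

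Three other places deal with worsening:

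- Protocol 11.1.1 includes in the AE definition an illness or disease that "has appeared or worsened during the course of the clinical trial, regardless of causal relationship" to the product.
- Protocol 8.3.2, on physical examination and vital signs, states: "Clinically significant changes from Baseline will be captured as AEs".
- Both definitions of a treatment-emergent event cover worsening. Protocol 12.7.2 adds "or worsening of an AE with an onset prior to first IP application" to events that start on or after first application. SAP 6.4.2 adds "or if the worsening of an event is during the on-treatment period".

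Seriousness has other routes in 11.1.3, among them: "Is a medically important event that may not be immediately life threatening or result in death or hospitalization, but may jeopardize the subject".

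**The concern.** Safety and tolerability are the primary objective (Protocol 5.1, SAP 2.1). There is one arm, and all summaries are descriptive. With no concurrent comparison to show that SAEs are being under-counted, the count depends directly on the rule that classes an event as serious.

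The exemption is sensible for an operation already booked when the subject enrolled, or for a stable condition treated at a convenient time. Its wording goes further. It covers any condition present at Screening, including one whose deterioration on the gel is the reason for the operation.

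Two features of this study widen its reach. First, Study 301 subjects are screened after their End of Treatment visit in that study (Protocol 8.1), so a condition that first arose on active gel in the parent study counts as present at Screening here. Second, treatment may continue past 12 months, which leaves more time for elective operations. Appendix 17.2 also lists features of the syndrome other than BCC, for example "Odontogenic keratocysts of the jaw confirmed histologically", that a subject may bring into the study.

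At stake are the serious flag, the row in the SAE tables and prompt notification of the sponsor for events in this class.

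**Working it through.** The plan gives no figure on this point, so the check is to follow one type of case through the definitions. Take a non-BCC condition recorded at Screening that worsens after first application and is treated by an elective inpatient operation.

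1. **Is the worsening an AE?** Yes. Section 11.1.1 covers disease that worsens during the trial, whatever the cause. The parenthesis in 11.1.3 has the hospitalization as its subject, not the condition or its worsening, so it does not cancel this.

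2. **Is it treatment-emergent?** Yes, although the added limb of Protocol 12.7.2 fits poorly. That limb speaks of an AE that began before first application, and AEs are collected only from consent (11.1.2), so a medical-history condition is not strictly one. But the worsening is itself an AE under 11.1.1, with an onset after first application, which meets the first limb. SAP 6.4.2 reaches the same result for the on-treatment period, which runs to 30 days after the last application (SAP 5.2.3).

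3. **Is causality recorded?** Yes. Sections 11.1.2 and 11.1.5 require it for every AE, serious or not.

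4. **Is it serious through hospitalization?** No. The parenthesis takes the admission out of that criterion, and nothing brings it back when the condition has worsened.

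5. **Is it serious by another route?** Perhaps. Death, threat to life, lasting disability and medical importance all remain available. The last depends on the investigator's judgement, and a scheduled operation will not always qualify.

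6. **What follows if no other route applies?** SAP 6.4.2 takes seriousness from the investigator's entry on the AE eCRF page, and SAP 6.4.2.4 builds the SAE tables and listings from it. Protocol 11.1.6 requires notification within 24 hours, and an entry in the safety database, for SAEs only. An event not flagged serious gets none of these. It appears as a non-serious TEAE by system organ class, preferred term, maximum severity and relationship (SAP 6.4.2.1).

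7. **Direction and unit of size.** Let N be the number treated, S the subjects reported with an SAE, and k the further subjects whose only serious event is of this kind. The reported proportion is S/N; with the exemption limited it would be (S + k)/N. The difference is k/N, which cannot be negative, so any bias lowers the SAE count. At the stated ceiling of about 200 subjects, each such subject is worth 1/200 = 0.5 percentage points, and more if fewer are treated. The documents give neither S nor k, so no total and no relative shortfall can be calculated.

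**The case against.** The strongest reply is that the parenthesis exempts an admission and nothing else. That is correct, and it rules out three stronger readings that a reader might infer.

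- **That the worsened condition is not an AE at all.** Section 11.1.3 makes this tempting, because the BCC sentence says the admission is not an SAE while the exemption says it is not an AE, which sounds wider. But the grammatical subject in both is the hospitalization, and 11.1.1 still makes the worsening an AE.
- **That the SAE tables omit on-treatment worsening of pre-existing disease in general.** They do not. Worsening that meets any other seriousness criterion, or that leads to an admission other than for elective surgery, is an SAE and is tabulated. Nor is the event lost before causality is assessed.
- **That a percentage can be put on the under-count.** It would need a rate of such operations and a number of other SAEs, and the documents supply neither.

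It is also fair to say that the exposed group should not be overstated. Inclusion criterion 5 requires BCCs plus one further major or two minor criteria; it does not require a jaw keratocyst or an ovarian fibroma. Appendix 17.2 is a diagnostic list and says nothing about progression or surgery. BCC, which every subject has, is governed by separate and explicit rules in 8.3.2, 11.1.2 and 11.1.3, so any non-reporting of BCC surgery does not come from this exemption.

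What the reply does not remove is step 4. The exemption is a stated rule without a worsening qualifier, and once it has been applied no later step restores the serious flag.

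**Conclusion.** The point holds in a narrow form. The plan contradicts itself on one class of event: a non-BCC condition, present at Screening, that worsens on study and leads to an elective inpatient operation without meeting any other seriousness criterion. The AE definition recognises the worsening, while the exemption denies it the hospitalization criterion. Such an event stays visible as a TEAE, with severity, corrective treatment and causality recorded, but is absent from the SAE tables and from 24-hour SAE reporting.

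The number of subjects affected is unknown and may be small, possibly none. The direction is known: any effect lowers the SAE count. The conclusion assumes that sites apply 11.1.3 as written; sites that already treat a worsened condition as outside the exemption would lose nothing, but the text does not tell them to. It is worth correcting because it concerns a safety definition in a single-arm study with safety as its primary objective, and because the correction costs little.

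**What to change.** Reconcile 11.1.3 with 11.1.1 by replacing the parenthesis with wording to this effect: *An admission planned before consent, or for elective surgery on a condition that has not worsened since Screening, is not in itself an AE. If the condition has worsened since Screening, the worsening is an AE and a resulting admission counts under the hospitalization criterion.* Leave the sentence on BCC surgery unchanged, and repeat the rule in the eCRF completion guidelines so that sites apply it alike. The SAP needs no change, since it takes seriousness from the eCRF.

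The cost is a one-sentence protocol amendment, the matching line in the guidelines, and a judgement by the site on whether the condition has worsened. The reported SAE count may be slightly higher. Treatment, visits and data collection are not affected.

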11.1.4 Assessment of Severity

The severity assigned to an AE should be determined by the maximum severity of the AE. The categories described below should be used to estimate the severity of AEs:

- **Mild:** Transient or mild discomfort; no limitation in activity; no medical intervention/therapy required
- **Moderate:** Mild to moderate limitation in activity; some assistance may be needed; no or minimal medical intervention/therapy required
- **Severe:** Marked limitation in activity; some assistance usually required; medical intervention/therapy required; hospitalization or prolongation of current hospitalization possible; may be incapacitating or life threatening

11.1.5 Assessment of Causality

The Investigator should assess the relationship of the AE, if any, to the IP. The following should be taken into account when assessing SAE causality:

- Positive temporal relationship to IP, such as if the IP was discontinued and the SAE resolved or the event recurred after re-introduction.
- If there is a reasonable possibility that the AE is associated with an underlying or concomitant illness.
- Possible association with previous or concomitant therapy.
- No temporal relationship to the IP and/or a more likely alternative etiology exists.
- If the AE is directly related to study procedures or a lack of efficacy.

The following classifications should be used when evaluating the relationship of AEs and SAEs to the investigational drug.

- 1. **Not Related**: No relationship between the experience and the administration of IP; related to other etiologies such as concomitant medications or subject's clinical state.
- 2. **Unlikely**: The current state of knowledge indicates that a relationship is unlikely.
- 3. **Possibly**: A reaction that follows a plausible temporal sequence from administration of the IP and follows a known response pattern to the suspected IP. The reaction might have

been produced by the subject's clinical state or other modes of therapy administered to the subject.

- 4. **Probably:** A reaction that follows a plausible temporal sequence from administration of the IP and follows a known response pattern to the suspected IP. The reaction cannot be reasonably explained by the known characteristics of the subject's clinical state or other modes of therapy administered to the subject.
- 5. **Definitely**: A reaction that follows a plausible temporal sequence from administration of the IP and follows a known response pattern to the suspected IP and can be confirmed with a positive re-challenge test or supporting laboratory data.

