6.2 Benefit-risk Assessment

Mitigation of BCCs and SEB tumor burden has so far been limited to avoiding sunlight, advice which is followed infrequently by patients at risk of developing sporadic skin tumors. Vismodegib, an orally bioavailable HHI has been studied for efficacy vs. BCCs in patients with Gorlin syndrome (Tang et al., 2012). In 41 patients followed for a mean of 8 months (range, 1 to

15) after enrollment, the per-patient rate of new surgically eligible basal-cell carcinomas was lower with vismodegib than with placebo

But because of detrimental class-specific side effects, most patients discontinue oral HHI such as vismodegib (John and Schwartz, 2016). Surgery is currently the definitive treatment for BCCs in patients with HF-BCC. Surgery has significant morbidity (e.g., scarring, functional loss of eyelid, nose, ear). Meanwhile, in Study Pelle-926-201, Patidegib Topical Gel, 2 % has shown promise to potentially mitigate tumor burden, without the systemic toxicity of oral HHI in patients with Gorlin syndrome.

The safety evaluation in the two clinical studies of the topical 2% and 4% formulations (Pelle-926-201, and Pelle-926-202) have shown that patidegib topical gel in repeated QD and BID doses appears to be safe and well-tolerated (Patidegib IB). Based on clinical and non-clinical studies for the topical product there are no known (expected) adverse events for the topical product. Adverse events and dermal safety and tolerability will nevertheless be monitored throughout the Phase 3 study.

Notwithstanding the low systemic bioavailability of Patidegib Topical Gel, 2%, (Patidegib IB) the class effects seen with oral HHI are considered potential adverse events for Patidegib Topical Gel, 2%. These include muscle spasm, alopecia and dysgeusia (Patidegib IB, Lacouture et al., 2016). As observed with the oral HHI class, embryo-fetal toxicity has been observed in nonclinical studies of the oral formulation of patidegib (Patidegib IB).

In non-clinical studies, changes in growth plate were observed in mice and young dogs treated at high doses. In skeletally mature adult dogs, there were no adverse bone changes (Patidegib IB). Cessation of growth in children treated with oral HHI has also been reported (Robinson et al., 2017). Pediatric patients are excluded from this study.

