11.1.6 Reporting of Serious Adverse Events

SAEs will be captured in both the clinical and safety database.

All SAEs, regardless of cause or relationship, that occurs after the subject first consents to participate in the study (i.e., signs the informed consent) and throughout the duration of the study and for 30 days following the last IP application will be captured in the clinical database via the eCRFs (Section 11.1.2).

SAEs also will be captured in the safety database. An initial SAE Report must be completed for all SAEs (irrespective of relatedness) with an onset date within 30 days from the date of last IP application. An initial SAE Report must also be completed for Related SAEs (possibly, probably or definitely) regardless of the time elapsed from the last dose (even if the study has been closed).

When new, significant information for an SAE is obtained, as well as when the outcome of an SAE is known, the Investigator must submit a Follow-Up Report. If the subject was hospitalized, a copy of the discharge summary must be included as part of the subject's medical file. For related events, the Investigator should monitor the subject until the outcome of the SAE is known. This may require periodic Follow-Up Reports.

PellePharm and the study CRO must be notified of all SAEs (regardless of causal relationship to IP) within 24 hours of the Investigator's knowledge of the event by faxing or emailing a completed SAE report to the CRO Medical Monitor.

If there are serious, unexpected AEs associated with the use of the IP, PellePharm (or designee) will notify the appropriate regulatory agency (ies) and all appropriate parties as appropriate (e.g., IRB) on an expedited basis. It is the responsibility of the Investigator to promptly notify the IRB of all unexpected SAEs involving risk to human subjects.

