11.1.8 Expedited Serious Adverse Event Reports

PellePharm will notify regulatory authorities of unexpected related SAEs and all participating study sites in writing for submission by the Investigator to the IRB, EC or REB. This notification will be in the form of a Safety Update to the IB (i.e., "15-day letter").

Upon receiving such notices, the Investigator must review and retain the notice with the IB and immediately submit a copy of this information to the responsible IRB/EC/REB, according to local regulations. The Sponsor, Investigator and IRB//EC/REB will determine if the informed consent requires revision. The Investigator should also comply with the IRB//EC/REB procedures for reporting any other safety information.

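### Read literally, all three causality grades counted as related require a known response pattern to the gel, so a new type of reaction has no related grade and related events may be undercounted

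*Protocol*

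**What the plan says.** Protocol section 11.1.5 gives a five-grade causality scale. Possibly and Probably both open with "A reaction that follows a plausible temporal sequence from administration of the IP and follows a known response pattern to the suspected IP". Probably adds that "The reaction cannot be reasonably explained by the known characteristics of the subject's clinical state or other modes of therapy administered to the subject". Definitely also asks for plausible timing, and that the reaction "follows a known response pattern to the suspected IP and can be confirmed with a positive re-challenge test or supporting laboratory data". Unlikely applies when current knowledge points away from a relationship. Not Related applies when there is no relationship and another cause accounts for the event.

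The three upper grades are the ones that count:

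- SAP section 6.4.2 defines related events by "Relationship with study treatment = Possibly / Probably / Definitely", and adds events whose relationship item was left unanswered.
- Protocol section 11.1.6 says "An initial SAE Report must also be completed for Related SAEs (possibly, probably or definitely) regardless of the time elapsed from the last dose".
- Protocol section 11.1.8 says "PellePharm will notify regulatory authorities of unexpected related SAEs".

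On what is known about the gel, Protocol section 6.2 states that "there are no known (expected) adverse events for the topical product". It then lists oral hedgehog-inhibitor class effects (muscle spasm, alopecia and dysgeusia among them) as potential events, and mentions embryo-fetal toxicity from non-clinical work. Protocol section 11.1.1 calls an event unexpected if the Investigator's Brochure does not list it, "or is not listed at the specificity or severity that has been observed".

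**The concern.** A single-arm extension has no concurrent control, so the investigator's attribution is the main causal information in its adverse event tables. Longer open-label use is also where a reaction not seen before could first appear. If every related grade asks for a pattern that is already known, while the protocol says the topical product has no known adverse events, then the scale is least able to record the very reactions the study should detect.

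At stake are the related-event outputs under the primary safety objective and the two reporting rules that turn on the word related.

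**Working it through.** The plan states no related-TEAE rate, so there is no figure to reproduce. The check is a comparison of definitions, followed by an illustration.

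**Step 1. Conditions for each grade (Protocol 11.1.5).** Let T = plausible timing, K = known response pattern, E = not reasonably explained by clinical state or other therapy, R = positive re-challenge or supporting laboratory data.

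| Grade | Needs | Counted as related |
|---|---|---|
| Definitely | T and K and R | yes |
| Probably | T and K and E | yes |
| Possibly | T and K | yes |
| Unlikely | knowledge points away from a relationship | no |
| Not Related | no relationship; another cause | no |
| Left blank | no answer | yes (SAP 6.4.2) |

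Every recorded related grade requires K.

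**Step 2. Cases run through the table.**

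- *New reaction, T met, K not met.* It fails all three related grades. Unlikely needs knowledge against a link, and Not Related needs another cause. Neither clearly applies, so no grade fits.
- *The same reaction, recurring on re-introduction.* R is now met but K is not, so Definitely still fails.
- *An oral-class effect such as dysgeusia.* Section 6.2 names it as potential. An investigator could treat that as K, which opens the related grades.
- *A local reaction monitored under section 8.3.1 (pain/burning, pruritus, erythema, edema, crusting).* Section 6.2 does not name these as known or potential events of the gel. Whether K is met depends on the reader.

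**Step 3. Outputs that depend on the grade.** In SAP 6.4.2.1, 4 of the 9 rows of the overall summary are restricted to related events (all, leading to discontinuation, serious, fatal). The other 5 are not. The table of TEAEs by relationship and the related SAEs by SOC and PT (SAP 6.4.2.4) also depend on it. In reporting, the exposed points are the section 11.1.6 report for related SAEs starting more than 30 days after last application, and the section 11.1.8 notice.

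**Step 4. Illustration of size.** N = 200 is the approximate maximum in the protocol synopsis. Two quantities are assumed: p, the true proportion of patients with a related reaction, and q, the share of those patients whose only related reaction lacks a known pattern and is recorded in an unrelated grade.

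Expected number graded related = N × p × (1 − q). Probability that none is graded related = (1 − p(1 − q))^N.

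| q | p = 2%: expected; P(none) | p = 5%: expected; P(none) | p = 10%: expected |
|---|---|---|---|
| 0 | 4; 0.018 | 10; <0.0001 | 20 |
| 0.25 | 3; 0.049 | 7.5; 0.0005 | 15 |
| 0.50 | 2; 0.134 | 5; 0.006 | 10 |
| 0.75 | 1; 0.367 | 2.5; 0.081 | 5 |
| 1 | 0; 1 | 0; 1 | 0 |

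Example: p = 5%, q = 0.5 gives 200 × 0.05 × 0.5 = 5 expected, against 10 true, and 0.975^200 = 0.006. The proportional undercount equals q. The documents give no value for q, so it can be anything from 0 to 1.

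**The case against.** A reader might infer that a new reaction must be graded unrelated, and that the related-TEAE result is therefore pulled to zero: 0 of 200 where the truth is, say, 10 of 200 (5%). The documents do not support that. A new reaction does not meet the wording of Unlikely or Not Related, so the text leaves a gap and does not force an unrelated grade. If the item is left blank because nothing fits, the SAP counts the event as related. The 0% result is the q = 1 extreme, which is an assumption.

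A reader might also infer that almost no event could be both unexpected and related. Section 11.1.1 rules that out, because an event is also unexpected if it "or is not listed at the specificity or severity that has been observed". A more severe form of a known pattern can be both. So can a class effect that is not listed as expected for the gel.

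Further points on the other side have weight. The protocol never defines a known response pattern or equates it with an expected event. It refers to an Investigator's Brochure that is not among the documents. Section 11.1.5 asks the investigator to weigh timing, resolution on stopping and recurrence. All SAEs go to the sponsor and CRO within 24 hours whatever the causality, and an SAE report is required for any onset within 30 days of last application. Section 11.1.6 also has its own expedited rule that does not use the five grades. TEAEs, serious TEAEs, discontinuations, deaths and dermal scores are summarized regardless of attribution.

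These points limit the harm but do not close the gap. The list of considerations is worded for SAE causality, and the grades are still the ones to be used for AEs and SAEs alike. A blank is missing data, not an option offered to sites: section 11.1.2 requires the causality assessment to be recorded. The named class effects leave out any other new reaction.

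**Conclusion.** The point holds as a gap in the scale. On a literal reading, a reaction outside any known pattern has no related grade, in a study whose primary objective is safety. The likely direction is an undercount of related TEAEs and related SAEs. Its size cannot be derived from the documents; for such events it runs from none to complete.

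This rests on two assumptions: that sites apply the definitions as written, and that they then choose an unrelated grade over leaving the item blank.

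The effect is confined to the related rows and tables, the report for related SAEs with onset beyond 30 days, and the section 11.1.8 trigger for unexpected related SAEs. A new reaction would still be counted and listed; only its attribution is at risk.

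**What to change.** In Protocol section 11.1.5, remove the known-response-pattern condition from Possibly. It could then read: the timing is plausible and a causal role of the IP cannot be excluded, although clinical state or other therapy could also explain the event. That gives a new reaction a related grade. A known pattern may stay as supporting evidence for Probably and Definitely. Because the SAP pools the three grades, the change to Possibly is the one that matters, and the SAP mapping needs no change.

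The cost is a protocol wording change, an updated eCRF completion guideline and a memo to sites. The related-TEAE rate may rise slightly. The change is best made before attributions are collected, because grades already recorded under the present wording are hard to reconstruct.
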